8.3.1. Time Period and Frequency for Collecting AE and SAE

All AEs and SAEs will be collected from the signing of the ICF until the final follow-up-visit (See Section 1.3).

Medical occurrences that begin before the start of study drug but after obtaining informed consent will be considered as pretreatment AEs.

All SAEs will be recorded and reported to Alexion immediately and under no circumstance should this exceed 24 hours, as indicated in Section 10.3. The Investigator will submit any updated SAE data to Alexion within 24 hours of awareness.

Investigators are not obligated to actively seek AE or SAE data after conclusion of the study participation. However, if the Investigator learns of any SAE, including a death, at any time after a participant has been discharged from the study, and he/she considers the event to be reasonably related to the study intervention or study participation, the Investigator must promptly notify Alexion.

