9.4.2. Safety Analyses

The primary objective of the study is to assess the safety and tolerability of ALXN1850. The endpoints to support the primary objective include incidence of TEAEs and treatment-emergent serious adverse events (TESAEs). The incidence of TEAEs and TESAEs will be summarized by System Organ Class (SOC) and Preferred Term by administration and cohort overall, by severity, and by relationship to study intervention. Adverse events will be categorized by the type of administration being received at the date of onset (ie, IV or SC). Treatment-emergent AEs and TESAEs resulting in withdrawal from the study will be listed. Participants having multiple AEs within a category (eg, overall, SOC, Preferred Term) will be counted once in that category. For severity tables, a participant's most severe event within a category will be counted. Adverse events of special interest will be analyzed similarly.

Changes from baseline in vital signs and laboratory assessments (as displayed in Table 7) will be summarized by visit for each cohort. Laboratory parameter values will be graded based on the National Cancer Institute CTCAE grading for severity (v5.0, published 27 Nov 2017). Shift tables by treatment group will be produced for these laboratory parameters. These tables will summarize the number of participants with each baseline grade relative to the normal ranges and changes to the worst highest grade assessed postdose during the study.

Electrocardiogram parameters will be measured at the specified time points, including heart rate, PR, RR, QRS, QT, and QTcF intervals. The average of the triplicate ECG readings at the time points collected will be calculated, and changes from pretreatment baseline values will be assessed.

An outlier analysis will be performed that will summarize the frequency and percentage of participants who meet any of the following outlier criteria at each visit.

- QT, QTcF interval > 450 msec
- QT, QTcF interval > 480 msec
- QT, QTcF interval > 500 msec
- QT, QTcF interval increases from baseline > 30 msec
- QT, QTcF interval increases from baseline > 60 msec

Physical examination results will be classified as Normal, Abnormal Not Clinically Significant (NCS), Abnormal Clinically Significant (CS), and Not Examined. The results will be summarized by visit for each administration.

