10.3.4. Recording and Follow-Up of AE and/or SAE

Recording of AE and/or SAE

• When an AE/SAE occurs, it is the responsibility of the Investigator to review all documentation (eg, hospital progress notes, laboratory reports, and diagnostics reports) related to the event.

Recording of AE and/or SAE

- The Investigator will then record all relevant AE/SAE information in the eCRF.
- It is not acceptable for the Investigator to send photocopies of the participant's medical records to Alexion or designee in lieu of completion of the AE/SAE eCRF page.
- There may be instances when copies of medical records for certain cases are requested by Alexion or designee. In this case, all participant identifiers, with the exception of the participant number, will be redacted on the copies of the medical records before submission to Alexion or designee.
- The Investigator will attempt to establish a diagnosis of the event based on signs, symptoms, and/or other clinical information. Whenever possible, the diagnosis (not the individual signs/symptoms) will be documented as the AE/SAE.

Assessment of Intensity

The Investigator will make an assessment of intensity for each AE and SAE reported during the study and assign it to one of the following categories from National Cancer Institute CTCAE v5.0, published 27 Nov 2017:

- Grade 1: Mild (awareness of sign or symptom, but easily tolerated)
- Grade 2: Moderate (discomfort sufficient to cause interference with normal activities)
- Grade 3: Severe (incapacitating, with inability to perform normal activities)
- Grade 4: Life-threatening
- Grade 5: Fatal

Changes in the severity of an AE should be documented to allow an assessment of the AE duration at each level of intensity to be evaluated. Adverse events characterized as intermittent require documentation of onset and duration of each episode, if the severity of the intermittent event changes.

An event is defined as "serious" when it meets at least 1 of the predefined criteria as described in the definition of SAE, NOT when it is rated as severe.

Assessment of Causality

- The Investigator is obligated to assess the relationship between the study intervention and each occurrence of each AE or SAE. An Investigator causality assessment must be provided for all AEs (both nonserious and serious). This assessment must be recorded in the eCRF and on any additional forms, as appropriate. The definitions for the causality assessments are as follows:

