- If a participant dies during participation in the study or during a recognized follow-up period, the Investigator will provide Alexion or designee with a copy of any postmortem findings including histopathology.
- New or updated information will be recorded in the originally completed eCRF.
- The Investigator will submit any updated SAE data to Alexion or designee within 24 hours of receipt of the information.

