9.1. Adverse Events

An adverse event (AE) is any untoward medical occurrence in a participant or clinical investigation participant administered a pharmaceutical product and which does not necessarily have to have a causal relationship with this treatment. An AE can therefore be any unfavorable and unintended sign (including an abnormal laboratory finding), symptom, or disease (new or exacerbated) temporally associated with the use of study intervention, whether or not considered related to the study intervention.

Adverse events will be analyzed in terms of TEAEs which are defined as any AEs that begin or worsen on or after the first dose of treatment until the final follow-up visit. If the onset date/time of an AE is missing and AE end date is on or after the first dose of treatment, the AE will be defined as treatment-emergent.

A treatment-related TEAE is defined as a TEAE that is considered to be related to the treatment.

A serious AE (SAE) is defined as any untoward medical occurrence that, at any dose, results in death, is life-threatening, requires inpatient hospitalization or prolongation of existing hospitalization, results in persistent disability/incapacity, is a congenital anomaly/birth defect, or are other situations (medical or scientific judgment should be exercised in deciding whether SAE reporting is appropriate in other situations such as important medical events that may not be immediately life-threatening or result in death or hospitalization but may jeopardize the participant or may require medical or surgical intervention to prevent one of the other outcomes listed in the above definition. These events should usually be considered serious).

The AE's relationship to study treatment will be evaluated by the investigator. The following relationships will be collected on eCRF: related or not related.

The AEs that are evaluated as related will be considered treatment-related AEs for summary purpose.

The severity of AEs will be classified by the investigator as mild (Grade 1), moderate (Grade 2), severe (Grade 3), 1 ife-threatening (Grade 4), or fatal (Grade 5).

Injection/infusion-site reactions are defined as AEs localized to the site of IV or SC route of study drug administration, occurring at any time during study participation that are assessed by the Investigator to be related to study drug.

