Injection/infusion-associated reactions are defined as systemic AEs (eg, fever, chills, flushing, alterations in heart rate and blood pressure, dyspnea, nausea, vomiting, diarrhea, and generalized skin rashes) oc curring during or within 24 hours of the start of IV or SC injection/infusion that are assessed by the Investigator to be related to the study drug.

An overview summary of TEAEs will be provided and will include number and percentage of participants:

- With at least 1 TEAE
- With at least 1 TEAE related to study drug
- With at least 1 TESAE
- With at least 1 TESAE related to study drug
- Drug withdrawn due to a TEAE
- Drug withdrawn due to a TEAE related to study drug
- Who died
- With at least 1 injection/infusion-site reactions
- With at least 1 injection/infusion-associated reactions
- With at least 1 hypersensitivity reaction

All AE summary tables will be summarized by the most recent type of administration (IV or SC), cohort, and overall (within each cohort and all cohorts combined)

All AEs will be coded using MedDRA (version to be delineated in the CSR). The summary will be presented according to the most recent type of administration (ie, IV or SC) be ing received prior to the AE onset regardless of when the AE ended, and by cohort and overall.

The TEAEs will also be summarized by system organ class (SOC), p referred term (PT), by severity and relationship to study treatment. The TESAEs will also be summarized by SOC, PT, and by relationship to study treatment.

Adverse events of special interest including injection/infusion-site reactions and hypersensitivity including anaphylaxis (injection/infusion-associated reactions [IAR] + hypersensivity) will also be summarized by SOC and PT.

The summary of TEAE, TESAE, and AE of special interest including injection/infusion-site reactions and hypersensitivity including anaphylaxis by SOC and PT will also be repeated by ADA status (ADA negative and ADA positive, and/or pre-existing immunogenicity, treatment-emergent ADA responses, and treatment-boosted ADA responses if data permits).

In the summary tables where both SOC and PT are presented, the default ordering of SOC will be alphabetical and the default ordering for PT will be most prevalent (using percentage) PT within each SOC based on Total column. For PTs with the same number of participants, they should be further sorted by number of events and then alphabetically.

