All summary tables will include number and percentage of participants and number of events, unless otherwise stated. For the number of AEs, each occurrence will be counted once. Percentages will be based upon the number of participants in the Safety Set.

In the by participant analyses, a participant having the same event more than once within the same level of summarization will be counted only once within the same administration (ie, IV or SC) using the most intense or severe event (for by toxicity grade summary) or the most related event (for by relationship summary).

All AEs will be listed from the signing of the ICF until the final follow-up visit.

Treatment-emergent AEs, TESAEs, TEAEs resulting in withdrawal from the study, injection/infusion-site reactions, hypersensitivity including anaphylaxis will be listed separately.

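### SAP 9.1 assigns TEAEs to IV or SC by onset alone, so some worsening events have no route and a grade reached after an SC dose can be shown under IV

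*SAP*

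**What the plan says.** SAP 9.1 analyses adverse events as TEAEs, meaning "any AEs that begin or worsen on or after the first dose of treatment until the final follow-up visit". An event can therefore qualify by starting after the first dose or by getting worse after it.

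The same section splits every AE summary table by the most recent type of administration, IV or SC, "received prior to the AE onset regardless of when the AE ended, and by cohort and overall". Protocol 9.4.2 sets the same anchor: "Adverse events will be categorized by the type of administration being received at the date of onset (ie, IV or SC").

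For participant counts by severity, SAP 9.1 says that repeated events at one level of summarization "will be counted only once within the same administration (ie, IV or SC) using the most intense or severe event". Event counts appear alongside, with each occurrence counted once.

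Three parts of the protocol bear on what onset means in the data:

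- Section 8.3.1: "Medical occurrences that begin before the start of study drug but after obtaining informed consent will be considered as pretreatment AEs".
- Section 10.3.4, on intensity: "Changes in the severity of an AE should be documented to allow an assessment of the AE duration at each level of intensity".
- Section 10.3.4, on follow-up: "New or updated information will be recorded in the originally completed eCRF".

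**The concern.** The treatment-emergent flag has two arms, starting and worsening. The route rule uses only the start. An event admitted by the worsening arm is therefore placed by a date that is not the one that made it treatment-emergent, and that date may come before any dose.

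The primary objective names both the single IV dose and the three weekly SC doses, and weekly SC dosing is the regimen the trial is meant to inform (Protocol 4.2). Readers will use the IV and SC columns to judge how each route was tolerated. Because IV always comes first, the rule can move severity in one direction only: a grade first reached in the SC period can be shown under IV, never the reverse.

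**Working it through.** No figure in the plan is in question, so the check is to apply the written rules in order to possible event histories.

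**Inputs**

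- Dosing days (Protocol Table 3). First participant in a cohort: IV Day 1, SC Days 15, 22 and 29. Subsequent participants: IV Day 1, SC Days 8, 15 and 22.
- Step 1, flag (SAP 9.1): TEAE if the event begins or worsens on or after first dose.
- Step 2, route (SAP 9.1): last administration before onset.
- Step 3, grade (SAP 9.1): worst grade within that route.
- Assumption: a continuous event that worsens stays one record with its first start date. Protocol 10.3.4 points this way, since it describes changing intensity within one AE and sends updates to the original eCRF, but it does not state it.

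**Applied to a subsequent participant**

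| Case | Onset | Worsens | TEAE? | Route under SAP 9.1 | What the tables show |
|---|---|---|---|---|---|
| A | Day 10 | no | yes | SC | correct |
| B | Day 5, Grade 1 | Day 10, Grade 3 | yes | IV | Grade 3 under IV, nothing under SC |
| C | Day -3 | Day 2 | yes | none: no dose precedes onset | in neither route column |
| D | Day -3 | Day 10 | yes | none: no dose precedes onset | in neither route column |

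For the first participant in a cohort, case B arises when onset falls after the IV dose and before the Day 15 injection, with worsening after that injection.

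**What changes and what does not**

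- The TEAE flag makes no use of route, so all four cases count in the overall columns. Overall TEAE and TESAE incidence is unaffected.
- Event counts: case B leaves IV + SC equal to the total. Each case C or D event leaves IV + SC one short of it.
- Size per affected participant, at the planned numbers: 1/5 = 20 percentage points within a cohort and 1/15 = 6.7 points with all cohorts combined. These are maxima, reached when the participant has no other event in the same row and column.

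**A neighbouring gap.** SAP 9.1 also makes an event with missing onset treatment-emergent if it ends on or after first dose, and SAP 4 rules out imputation. Such an event likewise has no derivable route.

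**The case against.** The strongest reply is that the key premise is not written down. The SAP says AE onset, not first-ever onset. Documenting duration at each intensity level is compatible with one dated record per grade, and eCRF completion rules are not part of these documents. If worsening is entered as a new record with its own start date, the problem disappears. This stands as a condition on the finding. Neither document says that it is done for continuous events, so the SAP as written does not settle the matter.

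The scope is also narrower than it may seem. Protocol 10.3.4 requires onset and duration for each episode of an intermittent event whose severity changes, and Protocol 10.3.1 makes an exacerbation of a pre-existing condition an AE in itself. Both carry their own onset. The no-route case is therefore mainly a continuous event that starts between consent and first dose and worsens later.

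Three stronger readings are tempting and are not supported:

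- **That the SAP contradicts itself.** It does not. The flag decides whether an event is included and the route rule decides its column. The onset anchor is shared with Protocol 9.4.2 and is a consistent convention that handles worsening badly.
- **That participant counts under IV and SC should add up to the overall count.** They need not, since a participant with events under both routes counts once in each. Only event counts expose the missing route.
- **That misplacement is frequent.** With assumed durations one can estimate how many events from the IV week are still open at the first SC dose. Only those that then worsen are affected, and the documents give no worsening rate.

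Finally, SAP 8.2 and 8.3 anticipate carryover of IV exposure into SC dosing, so a Day 10 worsening is not cleanly an SC effect. That limits what any route column can show about cause. It does not supply a route for cases C and D, or explain why a grade reached after an SC dose should appear only under IV.

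**Conclusion.** The point holds, conditionally. If a continuous AE that worsens keeps its first start date, SAP 9.1 and Protocol 9.4.2 together leave a TEAE that started between consent and first dose without an IV or SC column. They also show under IV a worst grade first reached after an SC dose, when the event began after the IV dose.

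The damage is confined to the route-split tables, mainly those by severity. A reader might infer that the primary endpoint or dosing decisions are at risk. They are not: overall TEAE and TESAE incidence is the same either way, the stopping rules in Protocol 7.1.1 and 7.1.2 turn on grade and relatedness with no use of these tables, and all AEs are listed individually. Frequency cannot be derived from the documents. The change is still worth making, because a single case is visible in cohorts of about five and the error runs in one direction.

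**What to change.** In SAP 9.1, and in Protocol 9.4.2 or with the departure from it noted:

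1. Assign route by the date and time the event became treatment-emergent: onset if on or after first dose, otherwise the first post-dose worsening. Cases A and B stay under SC and IV respectively, C goes to IV and D to SC.
2. In the severity-by-route table, place the worst grade under the administration most recently given before that grade was reached. The Grade 3 in case B then appears under SC.
3. Count each event once overall, in keeping with the counting rule already in SAP 9.1. Footnote events that began under IV and worsened under SC, and say that because of IV carryover the later route is not proof of cause.
4. In the same edit, give a default route for TEAEs with missing onset.

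The cost is SAP wording and minor programming. Protocol 10.3.4 already asks for severity changes to be documented, so no new data collection is needed. The one drawback is that an event can sit in one column of the incidence table and another column of the severity table, which the footnote explains.

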Hypersensitivity reaction labs (tryptase, IgE, C5b-9, chemistry, hematology, and urinalysis)	Х					$\leftarrow X^i\!\!\rightarrow$					
Concomitant medications			←Monitor	continual	ly after ICF is	signed→					
Adverse events review/evaluation	$\leftarrow Monitor continually after ICF is signed \rightarrow$										

Note: When scheduled at the same timepoint, the triplicate ECG should be performed first, followed by vital signs assessments, and then PK/PD sampling.

^a All postdose timepoints are relative to the start of the IV infusion/time of the SC injection (ie, time 0 hr) except the ECG, PK/PD sample, and infusion site evaluation performed/collected at the EoI (see footnote d).

^b Only if the Investigator approves the day prior as an Outpatient Visit.

^c Each 12-lead ECG will be performed in triplicate (sequentially within a 15-minute period) and should not be assessed after any major meal (ie, major meals should be withheld until after ECG assessments). At least the last of the 3 predose triplicate 12-lead ECG will be performed within half an hour prior to dosing. The ECGs at 2, 6, and 12 hours postdose have a window of \pm 30 minutes.

^d ECG and PK/PD (in that order) performed/collected at EoI (t_{max}) each have a window of + 15 minutes.

Protocol Amendment 5 10 Mar 2022

ALXN1850-HPP-101

- ^e Vital signs will be measured every 15 minutes for the first hour after dosing, with a window of \pm 5 minutes. Other vital signs measurements have a window of \pm 15 minutes.
- ^f A window of ± 30 minutes from each postdose time point is permitted for all PK/PD timepoints except EoI. Predose PK/PD windows are -1 hour (SC doses) and -3 hours (IV dose).
- ^g Injection/infusion site evaluations will be performed during the infusion, after I/EoI, and then within 15 minutes (+ 5 minutes) after I/EoI. The rest of the timepoints have a window of \pm 15 minutes.
- ^h Predose and postdose abbreviated PEs are allowed at the predose or dosing day, and on the day after dosing or 2 days after dosing, depending on when the participant is admitted and discharged.
- ⁱ If a hypersensitivity reaction is suspected, samples should be collected as soon as possible (within 1 hour of the reaction) and again at 2 and 8 hours (+ 1 hour window each) after the 1st sample. The Day 1 predose sample will only be analyzed for participants with a reported suspected hypersensitivity reaction at any time following the first dose.

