2.3.1. Risk Assessment

Potential risks of study participation include:

- Injection/infusion site reactions (ISRs)
- Injection/infusion associated reactions (including hypersensitivity)
- Formation of anti-ALXN1850 antibodies
- Ectopic calcifications

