8.3.6.2. Injection-associated Reactions

Injection-associated reactions are defined as systemic AEs (eg, fever, chills, flushing, alterations in heart rate and blood pressure, dyspnea, nausea, vomiting, diarrhea, and generalized skin rashes) occurring during or within 24 hours of the start of SC injection that are assessed by the Investigator to be related to the study drug. AE intensity reporting procedures are outlined in Section 10.3.4.

Page 54 of 97
Alexion Confidential

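### SAP 9.1 counts every injection/infusion-associated reaction under a hypersensitivity and anaphylaxis heading, and gives the protocol's own AESI no detailed table or listing

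*SAP*

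**What the plan says.** **Protocol.** Section 8.3.6 names two AESIs: injection site reactions and injection-associated reactions. Section 8.3.6.2 defines the second by symptoms ("Injection-associated reactions are defined as systemic AEs (eg, fever, chills, flushing, alterations in heart rate and blood pressure, dyspnea, nausea" and others), by a time limit ("occurring during or within 24 hours of the start of SC injection") and by the investigator's judgement that the event is related. Section 9.4.2, after describing the tables for treatment-emergent events by SOC and PT, adds: "Adverse events of special interest will be analyzed similarly". Hypersensitivity appears in the risk list of section 2.3.1 as part of another item ("Injection/infusion associated reactions (including hypersensitivity"). It also appears in the dosing-day schedule of section 1.3 as an event in its own right, with no 24-hour limit: "suspected hypersensitivity reaction at any time following the first dose".

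**SAP 9.1.** The definition is nearly the same, widened to IV dosing: "Injection/infusion-associated reactions are defined as systemic AEs (eg, fever, chills, flushing, alterations in heart rate and blood pressure, dyspnea, nausea, vomiting, diarrhea" and so on, related and within 24 hours. The overview table has one row for participants with an IAR and another for participants with a hypersensitivity reaction. The detailed AESI output then combines the two: "hypersensitivity including anaphylaxis (injection/infusion-associated reactions [IAR] + hypersensivity) will also be summarized by SOC and PT". That summary is repeated by ADA status. For listings, the SAP says: "injection/infusion-site reactions, hypersensitivity including anaphylaxis will be listed separately".

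**The concern.** An IAR is defined by timing, relatedness and a broad set of systemic symptoms. No allergic mechanism is required. A related Grade 1 nausea on the evening after a dose is therefore an IAR, and in the detailed AESI table it is counted under a heading that names anaphylaxis.

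This is a first-in-human study of an enzyme replacement, with antibody formation as a named risk and immunogenicity as a secondary objective. The AESI summary by ADA status is where a reader would look for a link between antibodies and allergic reactions. Nonspecific reactions mixed into that heading could suggest a link that is not there, or dilute one that is.

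The AESI that the protocol defines also loses its own detailed reporting. The IAR category is used elsewhere: the cohort rule in Protocol 7.1.1 on repeated Grade 2 events sets these reactions aside. A reader who wants to see which events fell into the category has no named listing to consult.

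**Working it through.** The plan states no figure to reproduce. The check compares definitions and outputs, with simple arithmetic for size.

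**1. Where each group is reported under SAP 9.1**

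| Output | IARs | Hypersensitivity |
|---|---|---|
| TEAE overview | own row | own row |
| AESI table by SOC/PT | only within the pooled group | only within the pooled group |
| Repeat by ADA status | only within the pooled group | only within the pooled group |
| AESI listing | none named | under the pooled group's label |

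The gloss that spells out the pooling appears once, at the SOC/PT table. The ADA-status repeat refers back to that summary. The listing sentence uses the label without the gloss, so it is not explicit whether IARs are in the listing.

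**2. How the two counts relate**

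Let I be the participants with an IAR and H those with a hypersensitivity reaction. The overview reports |I| and |H|. The AESI table reports |I ∪ H| under the hypersensitivity label. The difference from the overview's hypersensitivity row is

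|I ∪ H| − |H| = |I \\ H|,

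the number of participants with an IAR and no hypersensitivity reaction. It is never negative. It is zero only if every participant with an IAR also has a hypersensitivity reaction, and the IAR definition does not require that.

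**3. Size**

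The planned numbers are about 5 per cohort and about 15 in total (Protocol 1.1 and 9.2; SAP 4.2 for the total). One participant in I but not in H adds:

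- within a cohort: 1/5 = 20 percentage points;
- overall: 1/15 = 6.7 percentage points.

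The overview's hypersensitivity row does not move. If percentages in the ADA-status table are taken within ADA subgroups of a cohort, the denominator is at most about 5, so the step is at least about 20 points.

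**4. Is the hypersensitivity set defined?**

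SAP 9.1 defines site reactions and IARs but gives no definition or term list for a hypersensitivity reaction. Nearby wording does not settle it. SAP 9.8 ties analysis of the tryptase, IgE and C5b-9 samples to systemic acute hypersensitivity reactions. SAP 9.9 ties the same tests to an acute injection-associated reaction. Protocol 1.3 ties collection to a suspected hypersensitivity reaction. As written, neither the overview row nor the hypersensitivity part of the pooled group can be programmed reproducibly.

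**5. Does one term contain the other in the protocol?**

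The risk list in 2.3.1 places hypersensitivity inside IARs. The formal definition in 8.3.6.2 does not mention it and stops at 24 hours, while the schedule allows a suspected hypersensitivity reaction at any time after the first dose. A late reaction would be hypersensitivity but not an IAR, and a related early fever could be an IAR but not hypersensitivity. Under the working definitions neither set contains the other.

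**The case against.** The strongest defence is that the SAP discloses what it pools. The gloss states the sum, and its membership is largely that of the risk-list item in Protocol 2.3.1. The protocol's acute infusion reaction algorithm (10.6) also groups fever, flushing, urticaria, vomiting and bronchospasm together and grades infusion, allergic and anaphylactic reactions under one heading. A broad pooled screen is defensible in a small first-in-human biologic study. The overview keeps the two counts apart, the AESI table shows preferred terms (so nausea appears as nausea), all adverse events are listed, and about 15 participants can be read one by one. The primary endpoint is the incidence of TEAEs and TESAEs, and no stopping rule uses the pooled category.

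Most of this stands, and it limits the harm. It does not defend the label. Pooling is a reasonable choice, but the title should say what is pooled. Preferred terms do not tell a reader which events were judged allergic. The separate overview rows make the difference visible without explaining it, and they carry no breakdown by term or ADA status.

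Two stronger readings are tempting. A reader might infer that the protocol makes hypersensitivity a subset of IARs and that the SAP reverses the order. The documents do not support that: only the 2.3.1 risk list nests the terms, and 8.3.6.2 and the schedule do not. A reader might also infer that the SAP fails to report the protocol's AESI at all. It does report it, in an overview row and inside the pooled table. What is missing is a table or listing of its own.

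**Conclusion.** The point holds as a mislabelled pooled category with an undefined component. Followed as written, SAP 9.1 produces a rate headed as hypersensitivity and anaphylaxis, including by ADA status, that counts nonspecific related reactions and can exceed the overview's own hypersensitivity row. The possible gap is 20 points per affected participant in a cohort of five and 6.7 points overall. Whether any gap appears depends on at least one participant having an IAR that is not also classed as hypersensitivity; the documents give no expected rate. The sizes assume the planned enrolment.

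The effect is confined to the AESI table, its ADA-status repeat and, by label, the listing. The overview, the TEAE and TESAE summaries and the conduct of the trial are unaffected. It should be corrected because the ADA-status table bears on a named risk and the correction is small.

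**What to change.** In SAP 9.1:

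- Tabulate two separate AESIs by SOC and PT, and by ADA status: IARs as already defined, and hypersensitivity/anaphylaxis events. List each separately.
- State how a hypersensitivity reaction is identified (for example, a prespecified term list or an investigator-reported flag) and use the same rule for the overview row. Without this the split cannot be programmed.
- If a pooled output is still wanted, title it *IAR and/or hypersensitivity*.
- Align the terms with Protocol 2.3.1 and 8.3.6.2. The protocol definition covers SC dosing only and the SAP's covers both routes. The SAP already tabulates by most recent route, so its SC column can serve the protocol-defined AESI.

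The cost is SAP wording, one extra table (with its ADA-status repeat) and one extra listing. It uses data already collected and needs no new assessments. Counts in each table will be small, so they should be read as descriptions of individual cases.
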